3.2.1.2 Tumor Markers

Tumor Markers that are part of the trial site standard practices, as indicated by tumor type, are evaluated at timepoints coinciding with the CT/MRI imaging studies.

3.2.2 Pharmacodynamic, Biomarkers and Immunogenicity

These variables include:

- Archival Tumor Tissue for EGFR, HER2 and HER3 expression level, only applicable to patients included in Part 1
- Biomarkers: Potential biomarkers of interest include genes, gene transcripts, and proteins of the HER family receptors and molecules of the mitogen-activated protein kinase (MAPK) and phosphoinositide 3-kinase (PI3K) pathways involved in HER signaling. Peripheral blood samples are taken at Screening (after confirmation of eligibility); end of Cycle 2 (prior to dosing Cycle 3) or upon PD, whichever occurs first; EOT.
- Skin biopsy: All patients enrolled will undergo skin biopsies for evaluation of target-engagement (EGFR and HER3). Skin biopsy will be performed at Screening (after confirmation of eligibility), and end of Cycle 2 (prior to dosing Cycle 3) or upon PD,

PAREXEL International
Statistical Analysis Plan Template for Early Phase Studies

Symphegen A/S
Sym013-01

whichever comes first. Sampling procedure after amendment 6.0 (protocol version 7.0) was changed to Screening (after confirmation of eligibility) and Cycle 1, day 8 and Cycle 1 day 15.

- Tumor biopsy: Optional for Part 1 and required for Part 2, will be performed after confirmation of eligibility at Screening, and end of Cycle 2 (prior to dosing Cycle 3) or upon PD, whichever occurs first. Analysis of tumor biopsies will include target-engagement (EGFR, HER2 and HER3) and may furthermore include proteins and genes that are unknown or have not been included in the scientific hypotheses at the present time of trial, but that, during the collection of data from this trial, may evolve as new candidate genes and markers related to Pan-HER safety, efficacy, or mechanism of action.
- Immunogenicity (ADA): Analysis of ADA and residual serum levels of Pan-HER will be performed at a central laboratory. ADA will be assessed at C1/D1, C2/D1, Prior to every second cycle thereafter, EOT, 1M FUP.

3.2.3 Pharmacokinetic Variables

Serum concentrations of each of the 6 monoclonal antibodies (mAbs) that comprise Pan-HER will support the PK endpoints of the trial. The serum concentrations may also be used in an exploratory population PK analysis which will be reported separately from the clinical trial report.

PK blood sampling schedules are summarized in below tables (Table 11 and Table 12 from Clinical Study Protocol).

PAREXEL International
Statistical Analysis Plan Template for Early Phase Studies

Symphogen A/S
Sym013-01

Table 11 Schedule of Pharmacokinetic (PK) Assessments: Q1W Dosing

		Cycle 1				Cycle 2 Onward				EOT	1M FUP
Sampling Time	Window	D1-D3	D8	D15	D22	D1	D8	D15	D22		
Prior to SOI	- 4 h	X	X ¹								
EOI	+ 10 min	X	X ¹	X ¹	X	X ¹	X ¹	X ¹	X ¹		
EOI + 2 h	±30 min	X			X						
EOI + 4 h	±30 min	X			X						
EOI + 8 h ²	±90 min	X			X						
EOI + 24 h	±6 h	X			X						
EOI + 48 h	-12 h to + 24 h	X			X						
During Visit	NA									X	X

Abbreviations (in alphabetical order): D, day; EOI, End of Infusion; EOT, End of Treatment Visit; NA, Not Applicable; h, hour; min, minutes; 1M FUP, 1-Month Follow-up Visit; SOI, Start of Infusion

- 1) If Pan-HER dosing is delayed, only one PK sample should be taken during the visit.
- 2) Effective with Amendment 6, sampling at this timepoint is optional.

Table 12 Schedule of Pharmacokinetic (PK) Assessments: Q2W Dosing

		Cycle 1				Cycle 2		Cycle 3 Onward		EOT	1M FUP
Sampling Time	Window	D1-D3	D8	D15	D22	D1-D3	D15	D1	D15		
Prior to SOI	- 4 h	X		X ¹		X	X ¹	X ¹	X ¹		
EOI	+ 10 min	X		X ¹		X	X ¹	X ¹	X ¹		
EOI + 2 h	±30 min	X				X					
EOI + 4 h	±30 min	X				X					
EOI + 8 h ²	±90 min	X				X					
EOI + 24 h	±6 h	X				X					
EOI + 48 h	-12 h to + 24 h	X				X					
During Visit	NA		X		X					X	X

Abbreviations (in alphabetical order): D, day; EOI, End of Infusion; EOT, End of Treatment Visit; NA, Not Applicable; h, hour; min, minutes; 1M FUP, 1-Month Follow-up Visit; SOI, Start of Infusion

- 1) If Pan-HER dosing is delayed, only one PK sample should be taken during the visit.
- 2) Effective with Amendment 6, sampling at this timepoint is optional.

The PK endpoints with Q1W dosing will be derived based on the concentration time curves of Pan-HER after the first and fourth infusion of Pan-HER.

The PK endpoints with Q2W dosing will be derived based on the serum concentration time curves of Pan-HER after the first and third infusion of Pan-HER.

PAREXEL International
Statistical Analysis Plan Template for Early Phase Studies

Symphogen A/S
 Sym013-01

The planned PK endpoints are listed in Table 13 of Clinical Study Protocol.

The data may not allow for derivation of all endpoints for all mAbs, patients and occasions. C_{max} , C_{EOI} , C_{trough} and T_{max} will be derived from observed data while AUC_{τ} , $AUC_{\tau 0}$, $AUC_{norm, \tau}$, CL_s , CL_{ss} , V_s , V_{ss} , and $T_{1/2}$ will be estimated using non-compartmental methods and actual time points.

Table 13 Pharmacokinetic (PK) Endpoints, Definitions and Derivations

Symbol	Definition and derivation
C_{trough}	Trough concentration (i.e. concentration of Pan-HER measured pre-infusion)
AUC_{τ}	Area under the concentration-time curve in a dosing interval (i.e. from time zero (end of infusion) up to 168 hours). AUC_{τ} will be calculated using the linear trapezoidal method and interpolated in case of measurements after 168 hours, or extrapolated using terminal rate constant and the last quantifiable concentration
$AUC_{\tau 0}$	Area under the concentration-time curve from start of infusion up to 168 hours. $AUC_{\tau 0}$ will be calculated similar to AUC_{τ}
$AUC_{norm, \tau}$	Dose normalized area under the concentration-time curve in a dosing interval, calculated as AUC_{τ} divided by the dose infused
C_{max}	Maximum concentration
T_{max}	Time to reach maximum concentration
C_{EOI}	Concentration at End of Infusion
λ_z	Terminal rate constant (negative of the slope of an ln-linear regression of the un-weighted data considering the terminal phase of the concentration-time curve \geq limit of quantification). λ_z is not an endpoint, but is used for derivation of endpoints

PAREXEL International
Statistical Analysis Plan Template for Early Phase Studies

Symphogen A/S
 Sym013-01

Symbol	Definition and derivation
$T_{1/2}$	Terminal elimination half-life, calculated as $\ln(2)/\lambda_z$
CL_s	Clearance after first dose, calculated as Dose/AUC _{inf} for C1/D1, where AUC _{inf} will be calculated as the sum of the area from time zero to time of last quantifiable concentration, t_z , and the area from t_z to infinity. The second area will be estimated using the observed concentration at t_z and the terminal rate constant
CL_{ss}	Clearance after 3 rd /4 th dose, calculated as Dose/AUC _{τ}
V_s	Volume of distribution during the terminal phase after first dose (CL_s/λ_z)
V_{ss}	Volume of distribution during the terminal phase after 3 rd /4 th dose (CL_{ss}/λ_z)

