5.3.3 Treatment

On the day of the first scheduled Pan-HER infusion (C1/D1), and prior to the start of infusion (SOI), the Investigator must assess whether any changes have occurred in the clinical state of the patient, which would exclude the patient from the trial.

Pan-HER will be administered by IV infusion on either a Q1W or a Q2W schedule:

- Q1W: dosing will be every 7 (±2) days. Four (4) doses of Pan-HER administered Q1W constitute 1 cycle.
- Q2W: dosing will be every 14 (±2) days. Two (2) doses of Pan-HER administered Q2W constitute 1 cycle.

Patients in Part 1 will be enrolled to either Q1W or Q2W dose-escalation cohorts until establishment of an MAD, an MTD, and/or a RP2D for each schedule.

During Part 2, all patients will receive the RP2D and regimen of Pan-HER.

For all patients, the dose and schedule to be administered will be documented on the Screening and Allocation Form. Patients will receive the allocated dose and schedule according to their cohort assignment until treatment withdrawal. There will be no intra-patient dose-escalation. Dose-delays of Pan-HER and/or intra-patient dose-reduction(s) may be required upon occurrence of specific toxicities, as described in **Section 7.1.4**.

Treatment will continue until unacceptable toxicity or other conditions preventing further treatment, progressive disease (PD), termination of the trial, or patient's decision to withdraw.

Disease status evaluation will be by computed tomography (CT) or magnetic resonance imaging (MRI) according to Response Evaluation Criteria in Solid Tumors (Version 1.1) (RECIST v1.1) (22).

Confidential Page 41 of 156

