A safety monitoring committee (SMC) will be established and will include Investigator(s), Medical Monitor(s) and Sponsor's medical representatives. The SMC will review clinical and laboratory safety data regularly throughout the trial and will select the RP2D and regimen to be used in Part 2 based on safety data, as well as available PK and target engagement results.

[figure not shown]
The trial design is shown in Figure 1.

The overall Trial Plan is reported in Table - Overall Trial Plan.

PAREXEL International
Statistical Analysis Plan Template for Early Phase Studies

Symphogen A/S
Sym013-01

Figure 1 Overall Trial Design

Abbreviations: DLT: dose-limiting toxicity; G2T: grade 2 toxicity; MAD: maximum administered dose; MTD: maximum tolerated dose; P(): prophylaxis; RP2D: recommended phase 2 dose; Q1W: every week; Q2W: every second week.*

PAREXEL International
Statistical Analysis Plan Template for Early Phase Studies

Symphegen A/S
 Sym013-01

Table - Overall Trial Plan

Screening Period	
Screening	14 days within first dose of Pan-HER
Treatment Period	
Treatment Allocation	The allocated dose and schedule of Pan-HER will depend upon cohort assignment and will be confirmed by Sponsor or designee on the Screening and Allocation Form .
Pan-HER	
Pan-HER will be initiated on C1/D1 and based on cohort assignment, will be administered either Q1W or Q2W to separate dose-escalation cohorts of patients by IV infusion in cycles of treatment:
 
 • Q1W: Dosing on Day 1, 8, 15, and 22 of each 28-day cycle (± 2 days) • Q2W: Dosing on Day 1 and 15 of each 28-day cycle (± 2 days) 
The duration of infusion will be (effective with Amendment 5):
 
 • Minimum of 4 hours (+10 min) for all infusions. Titrated rate increases during infusions, and infusion duration reductions after C1/D1, will no longer be allowed. For Part 1 of the trial, Pan-HER will be administered following delivery of intensive prophylaxis, as defined herein, on a mandatory basis to reduce the risk of IRRs and oropharyngeal mucositis.
Discontinuation of Pan-HER	Treatment will continue until unacceptable toxicity or other conditions preventing further treatment, PD, termination of the trial, or patient's decision to withdraw.
End of Treatment	
End of Treatment Visit	Within 10 days after the decision to discontinue Pan-HER, an EOT Visit should be performed.

PAREXEL International

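### SAP Table 13 ends the dosing-interval AUC at 168 h on both schedules, so on Q2W (336 h interval) CLss and Vss are not what their formulas claim

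*SAP*

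**What the plan says.** SAP 3.2.3, Table 13, uses one set of definitions for both schedules:

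- AUCtau: "Area under the concentration-time curve in a dosing interval (i.e. from time zero (end of infusion) up to 168 hours".
- AUCtau0: "Area under the concentration-time curve from start of infusion up to 168 hours".
- AUCnorm,tau ("Dose normalized area under the concentration-time curve in a dosing interval, calculated as") is a ratio with AUCtau as its numerator and the dose given as its denominator, so it carries the same limit.
- CLss, after the third (Q2W) or fourth (Q1W) dose, divides the dose by the AUCtau above ("dose, calculated as Dose/AUC"). Vss is CLss/lambda_z.
- CLs and Vs, after the first dose, use AUC to infinity.

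The 168 h point itself has two branches. When a sample lies beyond that time, Table 13 says of the area that it "will be calculated using the linear trapezoidal method and interpolated in case of measurements after 168 hours". Failing that, the curve is carried forward to 168 h with lambda_z from the final measurable level.

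The Q2W schedule is stated elsewhere in the SAP as "Q2W: Dosing on Day 1 and 15 of each 28-day cycle", and Protocol 5.3.3 puts Q2W doses 14 (±2) days apart ("Two (2) doses of Pan-HER administered Q2W constitute 1 cycle"). SAP 4.10.4.1 defines both Q2W profiles as running from Day 1 to the Day 15 pre-dose sample. No section gives a 336 h limit. Protocol 10.4.4, Table 13, and the SAP abbreviation list repeat 168 h. The protocol's CLss and Vss refer to the fourth dose only; the SAP widened this to the third or fourth dose and left the limit alone. SAP 4.14 lists a PK change (reporting each antibody instead of the sum) but not this one.

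**The concern.** Dose divided by AUC over an interval estimates clearance at steady state only when the area covers the whole interval between doses. Table 13 satisfies this for Q1W and not for Q2W. It looks like an incomplete update: the dose number was revised when Q2W was accommodated, and tau was not.

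CLss for Q2W would appear in the same table as CLss for Q1W and as first-dose CLs (Dose/AUCinf). A difference in clearance between schedules, or between first and repeated dosing, could then come from the definition alone. The outputs concerned, Table 14.2.2 and Listing 16.2.6.2, are both starred for the abbreviated CSR, and the PK profile is a secondary objective. At Amendment 6, 3 + 7 + 3 = 13 of the 19 patients entered were on Q2W (Protocol 3.2.4.1).

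**Working it through.** **The plan's own figure.** Q1W: 7 x 24 = 168 h, which reproduces Table 13. Q2W: 14 x 24 = 336 h, which does not.

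**Inputs.** Dosing intervals from Protocol 5.3.3. Infusion time T = 4 h, the minimum since Amendment 5. Samples after the third Q2W dose from Table 12: end of infusion (EOI), then +2, +4, +8 (optional since Amendment 6), +24 and +48 h, and then nothing until the C2/D15 pre-dose sample. With infusion starts 336 h apart, that sample is at EOI + 332 h. Half-life: Protocol 3.2.3 gives 1 to 3 days in monkeys, rising with dose. No human value is given, so 1, 3 and 7 days is an assumed range.

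**Model.** One compartment, steady state, k = ln 2 / half-life. True CL = Dose/AUC from start of infusion (SOI) to SOI + 336 h.

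**Effect of the definition, integrating exactly.** The ratio of CLss to true CL factors into two parts:

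- truncation at 168 h: 1 + exp(-168k);
- starting at end of infusion, so losing the infusion area: kT / (1 - exp(-kT)).

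| Half-life | 1 day | 3 days | 7 days |
|---|---|---|---|
| Truncation factor | 1.008 | 1.198 | 1.500 |
| Infusion factor | 1.059 | 1.019 | 1.008 |
| Q2W CLss error, product | +6.7% | +22.2% | +51.2% |
| Q1W CLss error, infusion factor only | +5.9% | +1.9% | +0.8% |
| Q2W/Q1W CLss at equal true CL | 1.01 | 1.20 | 1.50 |

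Integrating from SOI to SOI + 168 h instead gives +0.8%, +20.3% and +50.6%. Vss = CLss/lambda_z carries the same error.

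**Effect of the interpolation rule.** The 168 h value falls in the gap between EOI + 48 h and EOI + 332 h. Table 13 names the linear trapezoidal method but no interpolation rule, and SAP 4.10.4.3 refers to sponsor procedures that are not shown. Applying each rule to the scheduled samples:

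| Half-life | 1 day | 3 days | 7 days |
|---|---|---|---|
| Linear interpolation: overstatement of AUC to EOI + 168 h | +46% | +19% | +5% |
| Linear interpolation: net CLss error | -26.9% | +2.5% | +43.6% |
| Same, +48 h sample drawn at the end of its window (+72 h) | -13.3% | +10.1% | +46.5% |
| lambda_z extrapolation from +48 h: net CLss error | +5.1% | +22.0% | +51.2% |
| EOI level / pre-dose level | about 14,600 | 24 | 4 |

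The extrapolation row applies if the Day 15 sample is below quantification. The last row shows this is likelier at 1 day than at 3 or 7 days.

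**Is steady state the cause instead?** The third Q2W dose reaches 1 - exp(-3 x 336k) of steady state: 98% at a 7-day half-life. The fixed limit is the main source of error.

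**Check of the remedy.** SOI to SOI + 336 h, linear up and logarithmic down, on the same samples: error at most 0.1% at all three half-lives. Extending the end-of-infusion area to the Day 15 pre-dose sample with linear trapezoids throughout would instead give CLss ratios of 0.59, 0.76 and 0.93. Both tau and the trapezoid rule need changing.

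**The case against.** The strongest objection is about size and sign. The SAP specifies linear trapezoids, so with a quantifiable Day 15 sample the natural reading is linear interpolation. On that reading the reported Q2W CLss is too low or about right over the only half-lives in the documents (-27% at 1 day, -14% at 2 days, +3% at 3 days). The +50% needs a 7-day half-life that no section supports, and one mono-exponential model cannot represent six antibodies whose PK the SAP itself calls dissimilar. This stands as a limit on the magnitude: neither size nor direction can be predicted for a given antibody. It does not rescue the definition, because two errors that partly cancel at some half-lives do not make an estimate of clearance.

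Second, the SAP describes CLss as clearance after the third or fourth dose and does not write steady state in the definition. That is fair, but dose over half an interval's area is not clearance under either description.

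Third, a common 168 h window is useful for comparing exposure between schedules. That is true of AUCtau, AUCtau0 and AUCnorm,tau as partial areas, which on Q2W are only mislabelled. It gives no ground for using such an area in CLss.

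Fourth, the consequences are limited. There is no hypothesis test, Part 2 did not take place, and concentrations are listed with actual times, so the values can be recomputed. If clearance depends on dose, first- and repeated-dose values could also differ with the right tau. These points keep the matter to secondary descriptive outputs.

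**Conclusion.** The concern holds. On Q2W, Table 13's dosing-interval area covers half the interval, and CLss and Vss computed from it are wrong by definition, whatever the half-life. The size depends on an unknown human half-life and an unstated interpolation rule. With exact integration from end of infusion the error is +7%, +22% and +51% at 1, 3 and 7 days; with linear interpolation to a quantifiable Day 15 sample it is -27%, +3% and +44%. These figures assume mono-exponential decline, steady state and a 4 h infusion. CLs, Vs, half-life, Cmax and troughs do not use the 168 h limit, and the DLT primary endpoint is unaffected. It should be corrected before the PK tables are run.

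**What to change.** In SAP Table 13, and in the matching entries of the SAP abbreviation list:

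1. Set tau = 168 h for Q1W and 336 h for Q2W in AUCtau, AUCtau0 and AUCnorm,tau, and hence in CLss and Vss.
2. Compute CLss as Dose/AUCtau0, from start of infusion over the full interval, with Vss = CLss/lambda_z. The C2/D15 pre-dose sample is already scheduled. If AUCtau from end of infusion is kept, end it at that pre-dose sample so that it does not run into the next infusion.
3. State linear-up/log-down trapezoids with log-linear interpolation in the declining phase, and lambda_z extrapolation to tau when the last sample is early or below quantification. This also covers actual intervals that differ from 14 days within the ±2-day window.
4. If a common exposure measure is wanted across schedules, report it separately as AUC0-168 and do not use it for CLss.
5. List the change from Protocol Table 13 in SAP 4.14.

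The cost is wording in Table 13 and the abbreviation list, one line in 4.14, and the NCA settings for tau and the trapezoid rule. No new samples or data collection are needed.

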Following the first administration of Pan-HER in monkeys, Pan-HER showed a rapid clearance from serum with short half-lives (T½) ranging from 1 to 3 days over the dose levels tested. A trend of increasing half-life with increasing dose was observed.

Dose-limiting toxicities (DLTs) in the form of diarrhea, dehydration and weight loss as well as skin sores/lesions were recorded after the second infusion of Pan-HER at 24 mg/kg and after one infusion at 36 mg/kg. The toxicity profile and PK profile indicate target engagement and that the toxicity is exaggerated pharmacology reflecting the mode of action of Pan-HER.

In the pivotal toxicology study, once-weekly IV infusions of Pan-HER to cynomolgus monkeys for six weeks at dose levels of 15 mg/kg/week or below were tolerated with no adverse signs of toxicity. Microscopically, there were no systemic findings, but locally thrombus formation and intimal proliferation within the saphenous veins were observed, and an increase in the inflammatory response in and around the infusion sites. These findings are considered as secondary toxicity features related to nonclinical immunotoxicity and not a direct target mediated toxicity.

Tissue cross reactivity studies showed specific positive staining with Pan-HER in the majority of human and cynomolgus monkey tissues examined. Specific positive staining with Pan-HER was observed mainly in tissues with epithelial and/or endothelial components and/or in the connective tissue.

Confidential Page 26 of 156

An *in vitro* safety study (i.e., a human whole blood activation assay using blood from six healthy donors) indicated that Pan-HER has a low risk of triggering acute immune toxicity in human blood as no significant increase in cytokine release was observed.

In conclusion, data from toxicology, tissue cross reactivity, PK and the *in vitro* safety study in human whole blood indicate that Pan-HER can be safely tested in human cancer patients. Based on the data described in the pivotal study, the No Observed Adverse Event Level (NOAEL) is considered to be 15 mg/kg.

For further information, refer to the Investigator's Brochure.

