4.10.4 Pharmacokinetics

4.10.4.1 Pharmacokinetic Concentrations

Serum concentrations for each of the six monoclonal antibodies in Pan-HER will be listed by mAb, dose schedule, dose group, patient, actual time relative to dosing, scheduled time and time deviation from scheduled time. The unit for the concentrations will be $\mu\text{g/mL}$.

Patient profiles serum concentrations vs. time points for each mAb will be plotted by dose schedule and dose group.

The following definitions are used for PK plots and tables:

PAREXEL International
Statistical Analysis Plan Template for Early Phase Studies

Symphegen A/S

Sym013-01

- First profile for weekly: all PK points from Cycle 1 Day 1 to Cycle 1 Day 8 (pre-dose)
- 2nd profile for weekly (4th dose): all PK points from Cycle 1 Day 22 to Cycle 2 Day 1 (pre-dose)
- First profile for biweekly: all PK points from Cycle 1 Day 1 to Cycle 1 Day 15 (pre-dose)
- 2nd profile for biweekly (3rd dose): all PK points from Cycle 2 Days 1 to Cycle 2 Day-15 (pre-dose).
- Dosing/sampling occasions for weekly dosing: Week 1, 2, 3, 4, 5, 6 etc., EOT, 1MFUP
- Dosing/sampling occasions for biweekly dosing: Week 1, 3, 5, 7, 9 etc., EOT, 1MFUP
- Peaks: serum concentration for each mAb assessed at EOI for each dosing occasion
- Troughs: serum concentrations for each mAb assessed prior to SOI for each dosing occasion

Violations of scheduled sampling will be reviewed on a patient by patient basis by Symphegen and PAREXEL. Following data review by Symphegen's pharmacokinetic expert, data points may be excluded from mean calculations and parameter calculation based on the below criteria:

- Individual outlying data points which are markedly deviating from the preceding and following time points
- Data points or PK profiles which are not compatible with known physiological processes underlying the PK properties
- Unexpected events or protocol deviations documented in e.g. laboratory notes or in protocol deviation reviews

Exclusions will be documented in the study files and the PC/PP files.

Following plots will be produced:

PAREXEL International
Statistical Analysis Plan Template for Early Phase Studies

Symphogen A/S

Sym013-01

- One panel per mAb, Dose Schedule and Dose group combination showing a profile for each patient: Patient Profiles for concentration vs. Actual Time by Dose Schedule and Dose Group (peak and trough for each dosing occasion) – Linear

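### For Q2W, the linear AUC rule overstates the third-dose AUC(0-168) more than the first-dose value, because only the first dose has a Day 8 sample, so the two tabulated values are not comparable

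*SAP*

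**What the plan says.** SAP section 3.2.3, Table 13, defines AUCtau as the area "from time zero (end of infusion) up to 168 hours", for Q1W and Q2W alike. The area "will be calculated using the linear trapezoidal method and interpolated in case of measurements after 168 hours". Where no later quantifiable measurement exists, the curve is instead extended from its final quantifiable value by means of the terminal rate constant. AUCtau0 is calculated in the same way, AUCnorm,tau is AUCtau divided by dose, CLss is dose divided by AUCtau, and Vss is CLss divided by the terminal rate constant.

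SAP Table 12 ("Schedule of Pharmacokinetic (PK) Assessments: Q2W Dosing") matches the protocol's Q2W schedule. After the first dose it has samples at EOI, +2, +4, +8 (optional), +24 and +48 h, a Day 8 visit sample, and the Day 15 pre-dose sample. After the third dose (C2/D1) the same early samples are followed only by the C2/D15 pre-dose sample. There is no Cycle 2 Day 8 column. The 48 h sample may be taken from 36 to 72 h.

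SAP section 4.10.4.1 places that late trough inside the third-dose profile: "2nd profile for biweekly (3rd dose): all PK points from Cycle 2 Days 1 to Cycle 2 Day-15 (pre-dose". Section 4.10.4.3 derives parameters for both profiles, per patient and per antibody. Table 14.2.2, which reports them, is marked for the abbreviated CSR.

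**The concern.** A straight line between two points on a convex declining curve lies above the curve. The wider the gap, the larger the overstatement. For Q2W, the first-dose profile has a real observation near 168 h, so its widest relevant gap is about 120 h. The third-dose profile has a gap of about 288 h, and the 168 h value inside it is interpolated. The same rule applied to both profiles therefore gives unequal errors, and the third dose looks more exposed than the first even with no true accumulation.

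Q1W does not have this asymmetry. Both of its profiles end with a pre-dose sample at about 168 h.

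The stake is the reading of the PK parameter table. Evaluating PK remains a secondary objective, and the antibodies are reported separately because their PK was found to differ. Since the error depends on half-life, it could also distort comparisons between antibodies.

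**Working it through.** The documents state no AUC or accumulation figure, so there is nothing to reproduce. The check applies the Table 13 rule to the Table 12 times.

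**Inputs**
- Sampling times after EOI: 0, 2, 4, 8, 24, 48 h; then 168 and 336 h for the first dose, and 336 h only for the third (SAP Table 12, nominal times).
- Half-life: protocol section 3.2.3 reports, in monkeys, "short half-lives (T½) ranging from 1 to 3 days over the dose levels tested". No human value is given, so 5 and 7 days are added as assumptions.
- Shape: mono-exponential, C(t) = exp(-kt), with k = ln 2 / half-life. True accumulation multiplies the whole third-dose curve by a constant, so it leaves the percentage bias unchanged.

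**Formulas**
- True AUC(0-168) = (1 - exp(-168k)) / k.
- First dose = trapezoids to 48 h + 120 × (C48 + C168)/2.
- Third dose: C168* = C48 - (C48 - C336) × 120/288; AUC = trapezoids to 48 h + 120 × (C48 + C168*)/2.

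**Worked case, half-life 2 days** (k = 0.01444 per h)
- Trapezoids to 48 h: 1.97 + 1.92 + 3.67 + 12.78 + 14.49 = 34.83.
- C48 = 0.5000, C168 = 0.0884, C336 = 0.0078.
- True: (1 - 0.0884)/0.01444 = 63.13.
- First dose: 34.83 + 120 × 0.5884/2 = 70.13, or +11%.
- Third dose: C168* = 0.5000 - 0.4922 × 120/288 = 0.2949, which is 3.3 times the true value; AUC = 34.83 + 120 × 0.7949/2 = 82.52, or +31%.
- Spurious factor: 82.52/70.13 = 1.18.

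**All half-lives**

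| Half-life (days) | First-dose bias | Third-dose bias | Spurious factor | True third/first ratio | Ratio under the SAP rule |
|---|---|---|---|---|---|
| 1 | +22% | +46% | 1.20 | 1.000 | 1.197 |
| 2 | +11% | +31% | 1.18 | 1.008 | 1.186 |
| 3 | +6% | +19% | 1.13 | 1.041 | 1.172 |
| 5 | +2.5% | +9% | 1.07 | 1.164 | 1.242 |
| 7 | +1.3% | +5.4% | 1.04 | 1.312 | 1.366 |

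**Sensitivity**
- Late sample at 72 h instead of 48 h: third-dose bias falls to +17% and +11% at 2 and 3 days.
- Trough at 332 h from EOI (4 h infusion): third-dose bias is almost unchanged, at +30.5% and +19.1% at 2 and 3 days.
- Bi-exponential examples: +3% to +8% (first) against +9% to +21% (third). Saturable-elimination examples: +2% to +23% against +15% to +57%.
- Trough below quantification: Table 13 switches to extrapolation with the terminal rate constant. The third-dose error is then about 0% to +1.5% for mono-exponential decline, and -11% to -15% in the bi-exponential examples. At a 1-day half-life the trough is 0.006% of peak, so this branch is the likely one there.

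**Clearance.** At steady state the true CLss is dose divided by the area over the 336 h interval. The reported-to-true ratio is therefore AUC(0-336) divided by the AUC used. At 2 days, AUC(0-336) = (1 - 0.0078)/0.01444 = 68.71. The ratio is 68.71/82.52 = 0.83 under the SAP rule, and 68.71/63.13 = 1.09 if only the interpolation is corrected.

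| Half-life (days) | 1 | 2 | 3 | 5 | 7 |
|---|---|---|---|---|---|
| CLss as written / true | 0.69 | 0.83 | 1.00 | 1.26 | 1.42 |
| CLss with the log rule, still cut at 168 h / true | 1.01 | 1.09 | 1.20 | 1.38 | 1.50 |

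**The case against.** Several points on the other side stand.

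- **Half-life.** The larger figures use monkey half-lives, and the protocol notes that half-life tended to rise with dose. At 5 to 7 days the spurious factor is modest.
- **Quantifiable trough.** The 1-day figures need a trough that would probably be below quantification. They should not be the headline.
- **Unseen procedures.** SAP section 4.10.4.3 refers to the sponsor's local non-compartmental procedures, which are not in the documents. Interpolation is not expressly called linear, but tied to the linear trapezoidal method that is the natural reading.
- **Other displays.** Peaks and troughs at every dosing occasion and individual semi-log profiles are reported, and they show accumulation without AUC. No accumulation ratio is planned, and all analyses are descriptive.
- **Expert review.** The SAP allows PK data points to be excluded after review and accepts that some endpoints may not be derivable. Neither provision corrects the interpolation rule.

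A reader might infer two stronger conclusions. The first is that Q2W steady-state clearance is falsely low. The inflated area does push CLss down, but stopping at 168 h in a 336 h interval pushes it up. In the check, the net error is low at 1 to 2 days, about nil at 3 days and high at 5 to 7 days. The second is that the choice of Part 2 regimen is affected. SAP sections 1 and 4.14 state that enrollment stopped in Part 1 and Part 2 did not take place. The documents support neither conclusion.

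**Conclusion.** The point holds for Q2W AUC(0-168). When the C2/D15 trough is quantifiable, the written rule overstates the third-dose value more than the first-dose value, and the two should not be read side by side. The direction follows from convexity and needs no particular elimination model. The size does depend on the model. Under mono-exponential decline with a sample at 48 h, the spurious factor is 1.18 to 1.13 at 2 to 3 days and 1.07 to 1.04 at an assumed 5 to 7 days. AUCtau0 and AUCnorm,tau inherit the bias.

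Q2W CLss and Vss are also unreliable, but with no fixed direction, because the 168 h cut-off and the interpolation work against each other. The consequence is confined to the PK parameter table of the abbreviated CSR. A correction is worth making because the table is still to be produced and the change is cheap.

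**What to change.** In SAP Table 13:
1. Use linear-up/log-down trapezoids, with log-linear interpolation at 168 h where no sample lies there, for both profiles and both schedules. For mono-exponential decline the third-dose bias becomes 0.0%; for other shapes some error across the long gap remains.
2. For Q2W, keep AUC(0-168) but label it a partial AUC.
3. Derive Q2W CLss and Vss from the area over the 336 h dosing interval with the same log-down rule. Step 1 alone is not enough: it would move CLss from 1.00 to 1.20 times true at 3 days, and further from true at 5 and 7 days.

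Record the departure from the protocol's Table 13 in SAP section 4.14. The cost is a few lines of SAP text, a standard setting in the non-compartmental software and one added area for Q2W. No extra sample is needed, since the C2/D15 pre-dose sample is already scheduled.
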